6.2 Subject Disposition and Data Sets Analyzed

The number of subjects screened, enrolled into the study, in each study population, who completed the study, and the reasons for any premature discontinuation from the study will be presented in summary tables by treatment group, by age strata (6 through 23 months, 24 through 47 months) and overall. The number in the full analysis set will be used as the denominator.

The number of subjects who are excluded from each of the FAS Immunogenicity and Per-Protocol populations will be summarized by treatment group, by age strata (6 through 23 months, 24 through 47 months) and overall.

6.3 Protocol Deviations

Major protocol deviations will be tabulated by vaccine group and will also be listed for subjects who have been entered into the study and assigned a subject number.

The following criteria will exclude a subject from the FAS population. These will be listed in the deviation listing:

- Not provided both pre- and post-vaccination blood samples
- Laboratory-confirmed influenza infection during the active period (Day 1 to Exit Visit)
- Received prohibited medication during the active study period which medically assessed to potentially impact immunogenicity results

Note: Other reasons for deviation may be added to this list, but will be done prior to unblinding of the study. The reasons highlighted will be used in defining the FAS population and per-protocol population.

6.4 Demographics and Other Baseline Characteristics

All baseline and demographic characteristics will be summarized by vaccine group, age strata, and overall on the FAS population. This will include age (months), gender, race, ethnicity, weight, height, BMI, pre-vaccination temperature, medical history, and previous vaccination status on the FAS population.

Derived variables:

Body Mass Index will be calculated according the following formula:

Body Mass Index (kg/m²): Weight (kg) / Height² (m²)

6.4.1 Medical History

Medical history will be coded according to Medical Dictionary for Regulatory Activities (MedDRA) version 22.0 or higher and will be displayed by system organ class and preferred term, using the MedDRA internationally agreed order.

The numbers and percentages of subjects with medical history will be presented by MedDRA system organ class (SOC) and preferred term (PT) by vaccine group and overall. Medical history data will be tabulated for FAS.

For prior vaccination history, the number and percentage of subjects who have ever been vaccinated, who have been vaccinated in the current season, and have been assigned to receive 1 or 2 vaccinations during the study, will be summarised.

6.4.2 Prior and Concomitant Medications

Medications will be coded using the WHO Drug dictionary version B3 MARCH 2019 or higher.

A prior medication is a medication used only before the first study vaccination (i.e. medication end date < first study vaccination date). Concomitant medications are all medications taken during the study period, including those started before but ongoing at vaccination.

When start and/or end dates of a medication intake are missing, the medication is considered as concomitant with the study vaccination schedule.

If the study vaccination date is missing, then the medication is considered as concomitant with the study vaccination schedule, provided that the study vaccine was administered to the subject.

Use of concomitant medication will be tabulated by treatment, age strata, therapeutic area, and preferred drug name.

Prior medications will only be listed.

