8.4.1.1 Concomitant Medications

Use of concomitant medication will be presented by treatment, age cohort, therapeutic area, and preferred drug name.

Concomitant medications are all medications taken during the study period, including those started before but ongoing at vaccination.

If a start date for a medication is partially or fully missing, and it is unclear as to whether the medication is prior or concomitant, it will be assumed that it is concomitant.

Medications will be coded using the WHO Drug dictionary.

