4.5.1 Important Protocol Deviations Leading to Exclusion from the PPS Analysis

A protocol deviation (PD) is any change, divergence, or departure from the study design or procedures of a study protocol. A protocol deviation may be a reason to remove data from an analysis set at the time of analysis. PDs can be either observable or programmable. Programmable PDs are those PDs that can be programmed from the data recorded in the clinical database. Observable PDs are PDs identified by CRAs or other team members.

PDs will be classified as major and minor using a prespecified list of types of deviations. Major PDs are defined in accordance with ICH E3 as important PDs related to study inclusion or exclusion criteria, conduct of the trial, subject management or subject assessment resulting in the potential to jeopardize the safety or rights of the trial subjects or the scientific value of the trial.

All PDs will be evaluated before unblinding and most will be classified into the following categories:

- Subject randomized and did not satisfy entry criteria
- Subject received the wrong treatment or incorrect dose
- Subject took an excluded concomitant medication
- Key study procedures missed or performed out of window, such as, for immunogenicity if the serum sample was collected outside the time window of 21 days the subject did not comply with the blood draw schedule and will be excluded from the PPS population. Hence, subjects will be excluded from PPS if blood draws >21 days after any vaccination.

The impact of major PDs on the efficacy, immunogenicity and/or safety results will be investigated by assessing the robustness of the study results.

Major PDs will lead to exclusion of the subject or part of the subject's data from at least one analysis set.

The number of subjects in any and by PD category will be summarized by treatment group, center and overall. Individual subject listings will be provided in an appendix, sorted by subject and by PD category.

Prior to unblinding the analysis, designated Seqirus staff will develop a memo that describes the PDs that led to exclusions from analysis sets. This memo will be signed off by at least the Biostatistician and the Clinical Scientist and will be included in the trial master file (Exclusion Memo).

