6.5.2.3 Analysis of Unsolicited Adverse Events

Definitions

All AEs will be characterized according to the date of occurrence related to the vaccination phase as follows:

- **Non-Treatment Emergent:** start date before the date of injection of study vaccine.
- **Treatment Emergent:** start date on or after the date of injection of study vaccine or, AE increase in severity, including to "serious" AE.

If start date is equal to the first date of injection, then "timing" variable ("Did event start before or after vaccination?") will be used to define whether the AE occur before or after the injection.

If an AE happened on the same day of injection and the time stamp is missing, then the AE is assumed to be treatment emergent.

If an AE start date is missing or unknown, the AE will be considered as emergent.

When start and/or end dates of an AE are only partially known, AEs will be categorized as emergent before, during, or after vaccination phase using the following rules:

- If the partial end date is before (<) the vaccination (i.e., year or year & month is/are before the study vaccination year or year & month) then the AE is not treatment-emergent before vaccination phase.
- If the partial start date is equal or after (≥) the first study vaccination (i.e., year or year & month is/are after or the same as the first study injection year or year & month) then the AE is considered treatment-emergent.

The **maximum event severity** is the greatest severity associated with a PT for a reported AE according to the following order: Mild < Moderate < Severe. Unknown/ Missing severity is considered as severe.

Multiple AEs with the same PT for the same subject are counted only once.

Vaccination-related AEs are those for which the cause has been evaluated by the investigator and recorded as related.

Analysis

This analysis applies to all Treatment-Emergent adverse events occurring during the study, judged either as probably related, possibly related, or not related to vaccination by the investigator, recorded in AE CRF, with a start date on or after the date of first vaccination. AE starting prior to the first vaccination will only be listed.

The original verbatim terms used by investigators to identify AEs in the CRFs will be mapped to preferred terms using the MedDRA dictionary. The AEs will then be

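### SAP 6.4.2 classes a medication known to have ended before vaccination as concomitant if its start date is missing, against its own definition and the protocol

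*SAP*

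**What the plan says.** SAP 6.4.2 gives a definition and then a rule for missing dates. The definition is: "A prior medication is a medication used only before the first study vaccination (i.e. medication end date < first study vaccination date"). The missing-date rule is: "When start and/or end dates of a medication intake are missing, the medication is considered as concomitant with the study vaccination schedule". The rule has no exception for an end date that is known. In the same section, concomitant medications go into tables ("Use of concomitant medication will be tabulated by treatment, age strata, therapeutic area, and preferred drug name"), while prior medications are listed and not tabulated.

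Protocol 8.4.1.1 has a narrower fallback with two conditions. The first is "If a start date for a medication is partially or fully missing". The second is "and it is unclear as to whether the medication is prior or concomitant, it will be assumed that it is concomitant". Both must hold before the default applies.

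SAP Section 7, on changes to the planned analysis, records one change, the renaming of the Evaluable Set. It says nothing about medication dates.

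SAP 6.5.2.3 has a related rule for adverse events: "If an AE start date is missing or unknown, the AE will be considered as emergent". For partly known dates, the same section treats an event whose end date falls before vaccination as not treatment-emergent.

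**The concern.** The two sentences in SAP 6.4.2 cannot both be applied to a medication that has a recorded end date before Day 1 and no recorded start date. The definition needs no start date, so the record qualifies as prior. The missing-date rule needs only one absent date, so the same record becomes concomitant. A programmer has to choose, and the literal text favours the second.

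Such records can be expected in principle. Protocol 6.5 asks sites to record medications from the month before the study, and it names longer look-back periods for some classes, such as systemic corticosteroids within 90 days of consent. A parent may remember when a course finished but not when it began.

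At stake is the accuracy of the concomitant-medication tables. They would report some drugs as taken during the study although the database shows that they had stopped beforehand.

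**Working it through.** The plan gives no figure on this point and there is nothing to recompute. The check applies each document's rule to every combination of known and missing dates, with the first vaccination as cut-off. Protocol 8.4.1.1 gives no date formula of its own. It counts a drug begun earlier as concomitant if it was still ongoing at vaccination, so a drug known to have stopped before then is not of unclear status.

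| Case | Start date | End date | SAP definition of prior | SAP missing-date rule | Protocol 8.4.1.1 |
|---|---|---|---|---|---|
| 1 | known | known, before vaccination | prior | not triggered | prior |
| 2 | missing | known, before vaccination | **prior** | **concomitant** | **prior** (status is clear) |
| 3 | missing | known, on or after vaccination | not prior | concomitant | concomitant |
| 4 | known, before vaccination | missing | cannot be judged | concomitant | fallback covers missing start dates only |
| 5 | known, on or after vaccination | missing | not prior | concomitant | concomitant |
| 6 | missing | missing | cannot be judged | concomitant | concomitant (status unclear) |

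- Cases 1, 3, 5 and 6: the SAP result is correct or agrees with the protocol.
- Case 4: the SAP default is a reasonable conservative choice and overrides no known end date.
- Case 2: the SAP rule overrides a date that is in the database. It disagrees with the SAP's own definition and with the protocol.

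So one case in six is wrong. The number of records in that case cannot be derived, because neither document gives a rate of missing medication dates.

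**Adverse events (SAP 6.5.2.3).** Three situations matter:

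1. Dates partly known, end before vaccination: not treatment-emergent, so an end-date check is already in place.
2. Start on the day of first injection: a timing variable decides whether the event came before or after vaccination, and a missing time leads to emergent.
3. Start date wholly missing, end date known and before vaccination: emergent, with no end-date check.

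Only the third has the same gap. Protocol 7.1 collects adverse events from consent, which may be given up to 10 days before Day 1, and analyses events before vaccination separately. An affected event would have to fall in that short interval and have a recorded end but no start.

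**The case against.** The best defence is about the order of application. Because the definition of prior needs only the end date, it could be applied first, with the missing-date sentence as a fallback for records it cannot classify. That reading removes the conflict and may be what was meant. The SAP does not state this order, however, and the sentence covers either date being missing, without exception. It is also fair that the rule is sound in the other five cases, and that a partly recorded start date need not count as missing under the SAP wording.

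A reader might infer that the misclassification produces false deviations and removes children from the Per Protocol Set, since SAP 4.5.1 lists the category "Subject took an excluded concomitant medication" and lets some deviations be programmed from the database. The documents do not support that:

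- Nothing links the 6.4.2 label to the deviation checks, and the recorded data in the case at issue include the early end date.
- The medication criterion in SAP 6.3 requires a prohibited drug received in the active study period and a medical assessment that it could affect immunogenicity.
- SAP 4.5 requires a medical assessment of impact before a deviation excludes a child from the Per Protocol Set, and SAP 4.5.1 has all deviations evaluated before unblinding.

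A false flag could arise only if a programmed check reused the 6.4.2 label, and no text says that it will.

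A reader might also infer that the adverse-event rule is wrong throughout. It is not, because the end-date check is there for partial dates. Nor is a bias between arms shown: the rule works on dates, not on treatment, in a randomized observer-blind trial.

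**Conclusion.** The point holds in a narrow form and is minor. SAP 6.4.2, read literally, gives a wrong classification when the start date is missing and the known end date precedes first vaccination. It contradicts the SAP's own definition, is broader than protocol 8.4.1.1, and is not declared in SAP Section 7. The affected drugs move from the prior listing into the concomitant tables.

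The conclusion assumes that the missing-date sentence takes precedence over the definition, as its wording suggests. The effect is confined to descriptive tables: the concomitant-medication tables and, in a case likely to be rare, the treatment-emergent adverse-event tables. No effect on the Per Protocol Set or on any of the eight co-primary comparisons is shown. No count of affected children can be given from the documents.

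**What to change.** In SAP 6.4.2, restore the protocol's condition and state the order of the rules:

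1. Class a medication as prior whenever its known or partial end date shows that it ended before first vaccination, whatever is known of the start date.
2. Class it as concomitant when the known start date or end date is on or after first vaccination, subject to rule 1.
3. Default to concomitant only when the available full or partial dates cannot settle the status.

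In SAP 6.5.2.3, extend the end-date check already used for partial dates to adverse events with a wholly missing start date: if the known end date is before first vaccination, the event is not treatment-emergent.

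If the sponsor prefers to keep the broader medication rule, SAP Section 7 should declare it as a change from protocol 8.4.1.1, and the definition of prior medication should be altered to match.

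The cost is a few lines in 6.4.2, one sentence in 6.5.2.3 and a small change to the derivation code. No extra data are needed, and I see no downside.

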6.5 Primary and Secondary Analysis

Derived immunogenicity variables:

Statistical Analysis Plan

Sponsor Name: Seqirus
Sponsor Protocol ID: V130_10

Values below the limit of quantification (recorded as "< LOQ") will be set to half that limit (LOQ/2).

The rate of seroconversion is defined as the percentage of subjects with either a prevaccination HAI (or MN) titer < 1:10 and a post vaccination HAI (or MN) titer ≥ 1:40 or a prevaccination HAI (or MN) titer ≥ 1:10 and a ≥ 4-fold increase in post vaccination HAI (or MN) titer.

All statistical analyses for HAI (or MN) titers will be performed on the logarithmically transformed (base 10) values. Individual HAI titers below the detection limit (<10) will be set to half of that limit (5). Individual MN titers below the lower limit of quantification (LLOQ), will be set to half of that limit (1/2* LLOQ).

Unadjusted for GMT, GMRs and pertaining two-sided 95% CIs will be calculated assuming log-normal distribution of the titers and will be completed by providing minimum, maximum and median titers for each vaccine group.

Seroconversion is defined as binary variable for subjects with non-missing values prevaccination and post-vaccination as:

= 1, if seroconverted (defined as the percentage of subjects with either a pre-vaccination HAI (or MN) titer < 1:10 and a post-vaccination HAI (or MN) titer ≥ 1:40 or a pre-vaccination HAI (or MN) titer ≥ 1:10 and a minimum 4-fold rise in post-vaccination HAI (Or MN) antibody titer)

= 0, otherwise

Geometric Mean Titer (GMT)

Serum HAI antibody levels of all participants will be determined in triplicate (HAI1, HAI2 and HAI3) on serum separated from the whole blood. Pre- and post-vaccination samples will be titrated in duplicate, simultaneously. The titer assigned to each sample shall be the geometric mean of three independent determinations i.e. Assigned titer= $\exp[(\log(\text{HAI1}) + \log(\text{HAI2}) + \log(\text{HAI3}))/3]$

GMT will be based on the following:

- HAI antibody titer for each strain: All analyses involving HAI antibody titer (namely group GMT within a vaccine group) will be performed on the log scale and the resultant summary statistic back-transformed to derived GMT

The GMT will be calculated using the following formula:

$$10^{\left[\frac{\sum_{i=1}^n \log_{10}(t_i)}{n} \right]}$$

where n , t_1 , t_2 , K , t_n are n observed immunogenicity titers.

The 95% confidence intervals for GMT will be calculated as $10^{\{M-t_{0.975,n-1}SE\}}$, $10^{\{M+t_{0.975,n-1}SE\}}$; where M and SE are the means and standard error of logarithm base 10 -transformed titers, respectively.

Geometric Mean Ratio (GMR)

GMRs measure the changes in immunogenicity titers *within* subjects.

The GMR will be calculated using the following formula:

$$10^{\left[\frac{\sum_{i=1}^n \log_{10} \left(\frac{t_{ij}}{t_{ik}} \right)}{n} \right]} = 10^{\left[\frac{\sum_{i=1}^n (\log_{10}(t_{ij}) - \log_{10}(t_{ik}))}{n} \right]}$$

where, for n subjects, t_{ij} and t_{ik} are observed immunogenicity titers for subject i at time-points j and k, $j \neq k$. The 95% confidence intervals for GMR will be calculated as $10^{\{M-t_{0.975,n-1}SE\}}$, $10^{\{M+t_{0.975,n-1}SE\}}$; where M and SE are the means and standard error of $\log_{10}(t_{ij}) - \log_{10}(t_{ik})$ respectively.

6.5.1 Analysis of Primary Immunogenicity Objective(s)

The primary immunogenicity objective of this study is to demonstrate that vaccination with Seqirus QIVc elicits an immune response that is not inferior to that of an US-licensed QIV containing the recommended strains for the season, in subjects 6 months through 47 months of age, as measured by HAI and MN.

6.5.1.1 Statistical Hypothesis

The non-inferiority of Seqirus QIVc compared to the US-licensed comparator QIV will be assessed by the 8 co-primary endpoints of GMT and SCR for A/H1N1, A/H3N2 and the B Strains. Definitions for noninferiority based on endpoints measured by HAI are derived from the FDA Guidance on seasonal inactivated influenza vaccines (Guidance for Industry Clinical Data Needed to Support Licensure of Seasonal Inactivated Influenza Vaccines 2007). A modified definition will be applied to assessment of the endpoint based on the MN assay.

The study will be considered successful if all the 8 co-primary endpoints are achieved. Specifically, Seqirus QIVc will be considered to be noninferior to the US-licensed QIV if, for each of the four strains, the following statistical criteria are met:

A/H1N1 and B strains:

- The upper bound of the two-sided 95% CI on the ratio of the HAI GMTs does not exceed 1.5. The HAI GMT ratio will be calculated as $\text{HAI GMT}_{\text{US-licensed QIV}} / \text{HAI GMT}_{\text{Seqirus QIVc}}$
- The upper bound of the two-sided 95% CI on the difference between the HAI SCRs does not exceed 10%. The difference in HAI SCRs will be calculated as $(\text{HAI Seroconversion}_{\text{US-licensed comparator QIV}} - \text{HAI Seroconversion}_{\text{Seqirus QIVc}})$. The 95% CI will be computed based on the binomial distribution.

A/H3N2 strain only:

Statistical Analysis Plan

Sponsor Name: Seqirus
Sponsor Protocol ID: V130_10

- The upper bound of the two-sided 95% CI on the ratio of the MN GMTs does not exceed 1.5. The MN GMT ratio will be calculated as $\text{MN GMT}_{\text{US-licensed QIV}} / \text{MN GMT}_{\text{Seqirus QIVc}}$
- The upper bound of the two-sided 95% CI on the difference between the MN SCRs does not exceed 10%. The difference in MN SCRs will be calculated as $(\text{MN Seroconversion}_{\text{US-licensed comparator QIV}} - \text{MN Seroconversion}_{\text{Seqirus QIVc}})$. The 95% CI will be computed based on the binomial distribution.

In mathematical notation the statistical hypotheses to be tested for the primary noninferiority immunogenicity analysis corresponds to:

- $H_0: R_i > 1.5$, for any strain
- $H_a: R_i \leq 1.5$, for all strain and
- $H_0: D_i > 10$, for any strain
- $H_a: D_i \leq 10$, for all strain

where R_i is any of the 4 strain-specific post immunogenicity dose GMT ratios:

- (US-licensed comparator QIV) / (QIVc) for B/Yamagata strain
- (US-licensed comparator QIV) / (QIVc) for B/Victoria strain
- (US-licensed comparator QIV) / (QIVc) for A/H1N1 strain
- (US-licensed comparator QIV) / (QIVc) for A/H3N2 strain

and D_i is the 4 strain-specific post-dose SCR difference, namely

- (US-licensed comparator QIV) - (QIVc) for B/Yamagata strain
- (US-licensed comparator QIV) - (QIVc) for B/Victoria strain
- (US-licensed comparator QIV) - (QIVc) for A/H1N1 strain
- (US-licensed comparator QIV) - (QIVc) for A/H3N2 strain

No adjustment of Type I error will be made for multiple comparisons.

6.5.1.2 Analysis Sets

The Per Protocol Set will be used for the primary immunogenicity analysis and a supporting analysis will be performed using the FAS – Immunogenicity Analysis. Duplicate tables of primary and secondary immunogenicity analyses may also be produced based on the FAS Immunogenicity population if there is >5% difference in the total number of subjects between the Per-Protocol Population and the FAS Immunogenicity Population.

